If the subject's COWS is ≥ 8 , they will complete the remaining pre-buprenorphine assessments including the following: vital signs, 12-lead electrocardiograms (ECG), AEs, and sedation using a Sedation VAS. Body weight and a blood sample for liver function testing (LFT) will also be collected at any time before dosing with SUBLOCADE.

If a subject's COWS is not ≥ 8 , the subject may either be re-scheduled for check-in within the Screening Period or remain in the clinic (at the Investigator's discretion), and the COWS may be repeated until the subject achieves a score ≥ 8 . Only when the COWS is

≥8 and all pre-buprenorphine assessments have been completed may the subject receive TM buprenorphine.

One hour after the 4mg TM buprenorphine dose, the subject will complete pre-SUBLOCADE assessments including: COWS (first, to assess precipitated withdrawal) and OC-VAS, then Sedation VAS, AEs, vital signs and concomitant medications.

Any subject who display any allergic/hypersensitivity reaction to buprenorphine will be discontinued from the study and will be followed up via telephone call 24 to 72 hours post dose.

Subjects experiencing precipitated withdrawal will be treated for withdrawal symptoms. If precipitated withdrawal occurs before SUBLOCADE administration, the TM induction may be restarted later on the same day at the discretion of the Investigator, based on the half-life of the opioid reported on the TLFB. Alternatively, the Investigator may permit the subject to return to the facility on another day (within the Screening Period). Returning subjects will repeat all Day 1 scheduled assessments.

If the subject experiences withdrawal symptoms at any time (including precipitated withdrawal after SUBLOCADE), he/she may be treated symptomatically ([SAMHSA TIP 63 2018](#)):

- nausea: ondansetron or metoclopramide
- diarrhoea: loperamide
- anxiety, irritability, sweating: clonidine
- insomnia: diphenhydramine, trazodone
- pain: nonsteroidal anti-inflammatory drugs

If the subject does not display any allergic/hypersensitivity reaction or clinical signs of sedation, and does not experience precipitated withdrawal, 300 mg SUBLOCADE may be administered to the subject. A blood sample will be collected prior to SUBLOCADE administration for NMP PK assessment.

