Sufficient subjects will be enrolled to ensure that 15 subjects are dosed with SUBLOCADE and are evaluable for precipitated withdrawal; that is, 15 subjects having data for at least 1 COWS assessment before SUBLOCADE injection and COWS assessments for 48 hours after SUBLOCADE injection.

Following SUBLOCADE (300 mg) administration, the subject will remain in the clinic for approximately 48 hours and will be assessed for safety and tolerability, as well as for any signs of precipitated withdrawal.

Blood samples for NMP PK assessment will also be collected as close to the nominal timepoint as possible. In addition, subjects will be assessed for the following: AEs, vital signs, 12-lead ECGs and concomitant medications. Subjects will also be examined for withdrawal symptoms within 48 hours of SUBLOCADE administration based on COWS,

opioid craving (using OC-VAS), and sedation (using Sedation VAS). The injection site will be assessed for signs of reaction or infection, which will be reported as AEs, if present.

Subjects who experience opioid withdrawal after SUBLOCADE administration may be treated with non-opioid medications as above ([SAMHSA TIP 63 2018](#)). Supplemental TM buprenorphine (after SUBLOCADE administration) may only be permitted after discussions with the medical monitor. Subjects will not be discontinued from treatment due to illicit opioid use (including buprenorphine).

Subjects will return to the clinic weekly, until the end-of-treatment (EOT) visit, to assess COWS, OC-VAS, AEs, vital signs and concomitant medications; the injection site will be assessed for any evidence of tampering and for any signs of reaction or infection. Subjects will also self-report their illicit drug use since last visit, including a TLFB, and provide a urine sample for UDS. A blood sample for NMP PK assessment and a blood sample for LFTs will also be collected. If LFT value increases are noted, additional testing should be performed as described in Section [8.2.7.3](#).

[figure not shown]
All subjects will receive counselling as determined by local standard of care throughout the study from Day 1 through EOT.

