4.3 Schedule of Assessments

An overview of the schedule of assessments for the study overall is provided in [Table 1](#) and the detailed schedule of assessments for the Injection Visit (Visit 2, Days 1-3) in [Table 2](#).

Table 1 Schedule of Assessments – Overview of Study

| Procedure/Assessment | Screening | Injection ^a | 1 week post dose | 2 weeks post dose | 3 weeks post dose | EOT ¹⁶ | EOS ¹⁷ | TM BUP ET ¹⁸ |
|---|------------------|------------------------|------------------|-------------------|-------------------|-------------------|-------------------|----------------------------------|
| Visit Number | 1 | 2 | 3 | 4 | 5 | 6 | 7 | |
| Day(s) | -30 to -1 | 1-3 | 8 | 15 | 22 | 29 | 43 | 24-72 hr Post-TM BUP dose |
| Window (days) | | | ± 1 | ± 2 | ± 2 | ± 2 | ±5 | |
| Informed Consent ¹ | X | | | | | | | |
| Inclusion/Exclusion Criteria | X | | | | | | | |
| Demographics | X | | | | | | | |
| Medical/Psychiatric History | X | | | | | | | |
| Substance/Drug Use History ² | X | | | | | | | |
| Physical Examination ³ | X | | | | | X | | |
| Height/Weight/BMI ⁴ | X | X ^a | | | | X | | |
| Vital Signs ⁵ | X | X ^a | X | X | X | X | | |
| 12-Lead ECG ⁶ | X | X ^a | | | | X | | |
| AE Assessment | ← X → | | | | | | | |
| Concomitant Medications ⁷ | ← X → | | | | | | | |
| HIV-1/HIV-2, Hep B, Hep C Antibody ⁸ | X | | | | | | | |
| Haematology | X | | | | | | | |
| Serum Chemistry | X | | | | | | | |
| Liver Function Testing ⁹ | | X ^a | X | | | X | | |
| Urinalysis | X | | | | | | | |
| Urine Pregnancy Test ¹⁰ | X | X ^a | | | | X | | |
| Alcohol Breath Test | | X ^a | | | | | | |

Table 1 Schedule of Assessments – Overview of Study

| Procedure/Assessment | Screening | Injection ^a | 1 week post dose | 2 weeks post dose | 3 weeks post dose | EOT ¹⁶ | EOS ¹⁷ | TM BUP ET ¹⁸ | |
|---|-----------|------------------------|------------------|-------------------|-------------------|-------------------|-------------------|---------------------------|--|
| Visit Number | 1 | 2 | 3 | 4 | 5 | 6 | 7 | | |
| Day(s) | -30 to -1 | 1-3 | 8 | 15 | 22 | 29 | 43 | 24-72 hr Post-TM BUP dose | |
| Window (days) | | | ± 1 | ± 2 | ± 2 | ± 2 | ±5 | | |
| UDS ¹¹ | X | X ^a | X | X | X | X | | | |
| Self-Reports/TLFB ¹² | | X ^a | X | X | X | X | | | |
| COWS | X | X ^a | X | X | X | X | | | |
| OC-VAS | X | X ^a | X | X | X | X | | | |
| Sedation VAS | | X ^a | | | | | | | |
| Study Drug Administration | | X ^a | | | | | | | |

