1. Upon arriving at the clinic, subjects will provide a urine sample for a UDS for qualitative and quantitative analysis, a urine sample for a pregnancy test (child-bearing females only), perform an alcohol breathalyser test and self-report their concomitant medications since screening and recent illicit drug use (including the use of a TimeLine Follow Back [TLFB]). If subject is deemed eligible for check-in the subject will then be assessed for withdrawal symptoms using COWS and for craving using OC-VAS.
 2. Details subjects illicit drug use, in addition to report question capturing frequency, route and date of last use.
 3. Required for female subjects of childbearing potential only.
 4. Per Investigator's discretion, subjects with positive test may either remain in the clinic or be re-scheduled to return on another date.
 5. Per Investigator's discretion, subjects with COWS <8 may either remain in the clinic and repeat assessments at a later time or be re-scheduled to return on another date. The COWS may be repeated at any time, per Investigator's discretion, and should always be repeated just before TM-BUP and SUBLOCADE administration. The OC-VAS should be performed each time a COWS assessment is performed.
 6. If the subject is asleep at 16 and 20 hours, the assessments will not be performed, and the reason should be noted in the CRF.
 7. Includes a review of any previous (taken since screening) and ongoing medications (including over-the-counter) and herbal supplements.
 8. Includes systolic and diastolic blood pressure, pulse rate, respiratory rate and oral temperature after the subject has been in a sitting position for ≥ 3 minutes.
 9. An ECG will be collected after the subject has been in a supine position for ≥ 5 minutes.
 10. Eligible subjects must meet the buprenorphine dosing criterion, prior to receiving 4mg TM buprenorphine.
 11. A sub-set of serum chemistry to be performed including: ALP, ALT, AST, bilirubin, albumin, total protein, GGT and LD only. For increased LFTs, subject should be asked to return to the clinic for weekly repeat liver chemistry testing (ALP, ALT, AST, and total bilirubin) until resolved, stabilised or return to within baseline values, per Section 8.2.7.3.
 12. Weight to be captured; BMI will be calculated in the database using height from screening.
 13. Assessment to be performed anytime pre-SUBLOCADE dose.
 14. Eligible subjects meet SUBLOCADE dosing criteria, prior to receiving SUBLOCADE.

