5.3 Exclusion Criteria

1. Current diagnosis, other than OUD, requiring chronic opioid treatment.
 2. Meet DSM-5 criteria for severe alcohol-use disorder.
 3. Has received any medication assisted treatment within 2 weeks.
 4. Concurrent or prior treatment with any long-acting depot form of buprenorphine-containing products.
 5. Concurrent treatment with another investigational agent or enrolment in another clinical study (except for an observational study) or treatment with another investigational agent within 30 days prior to screening.
-

6. Concurrent treatment with medications contraindicated for use with buprenorphine as per local prescribing information, including benzodiazepines or any other central nervous system depressants.
 7. Significant traumatic injury, major surgical procedure (as defined by the Investigator) within 30 days prior to Day 1 or still recovering from prior surgery.
 8. Any other active medical condition, organ disease or concurrent medication or treatment that may either compromise subject safety or interfere with study endpoints.
 9. Congenital long QT syndrome, history of prolonged QT in the 3 months prior to screening, or a corrected QT interval (Fridericia's – QTcF) >450 msec (male) or >470 msec (female), or history of risk factors for Torsades de Pointes. Known personal and/or family history of congenital QT prolongation, or taking Class IA antiarrhythmic medications (e.g., quinidine, procainamide, disopyramide) or Class III antiarrhythmic medications (e.g., sotalol, amiodarone) or other medications that prolong the QT interval. Known family history of sudden unexplained death.
 10. Total bilirubin $\geq 1.5 \times$ ULN, ALT $\geq 3 \times$ ULN, AST $\geq 5 \times$ ULN, serum creatinine $> 2 \times$ ULN at screening.
 11. Abdominal area unsuitable for SC injections (e.g., nodules, lesions, excessive pigment, infected, scarring).
 12. Uncontrolled intercurrent illness including, but not limited to, a medical or psychiatric illness/social situation that would limit compliance with study requirements or compromise the ability of the subject to provide written informed consent.
 13. Known allergy or hypersensitivity to buprenorphine, ATRIGEL or their excipients.
 14. Subject to court order requiring treatment for OUD.
 15. Subjects who are unable, in the opinion of the Investigator or Indivior, to comply fully with the study requirements including those who are currently incarcerated or pending incarceration/legal action.

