5.1.3 Definition of Pre-TM BUP Value, Pre-SUBLOCADE Value, and Pre-SUBLOCADE Baseline

For analyses of COWS and OC-VAS (i.e., the key and exploratory endpoints), the Pre-TM BUP value is the measure obtained at the Pre-TM BUP timepoint just before a TM-BUP dose for induction, and the Pre-SUBLOCADE value is the measure obtained at the Pre-SUBLOCADE timepoint just before the SUBLOCADE injection.

For the analysis of other safety assessments (described in Section 5.5), the Pre-SUBLOCADE baseline will be the last non-missing value prior to the administration of SUBLOCADE.

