5.5.8.5 Liver Function Tests

The absolute values and change from the pre-SUBLOCADE baseline of scheduled liver function tests (LFTs) will be summarised for the pre-SUBLOCADE baseline and the SUBLOCADE treatment period.

The frequency count and percentage of subjects meeting the protocol-specified liver chemistry review criteria (as below) will be summarized at pre-SUBLOCADE baseline and during the SUBLOCADE treatment period using assessments at both scheduled and unscheduled visits:

- ALT >3 × ULN and bilirubin >2 × ULN
- ALT >3 × ULN (and bilirubin ≤ 2 × ULN)
- ALT >5 × ULN but <8 × ULN
- ALT ≥8 × ULN

All LFT data (including unscheduled and re-check values if present) will be listed chronologically.

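### The liver table reports ALT above 3 × ULN as unlinked baseline and treatment-period totals, so it cannot separate continuing or chance elevation from new elevation

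*SAP*

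**What the plan says.** **Entry.** Protocol 5.3, criterion 10, excludes "ALT $\geq 3 \times$ ULN, AST $\geq 5 \times$ ULN" at screening, which Table 1 places on Days -30 to -1. A subject at 2.9 × ULN is eligible.

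**Dosing.** Protocol 4.1 says: "Body weight and a blood sample for liver function testing (LFT) will also be collected at any time before dosing with SUBLOCADE". The Table 2 footnote agrees: "Assessment to be performed anytime pre-SUBLOCADE dose". The three SUBLOCADE dosing criteria in Protocol 5.7 cover allergic reaction, precipitated withdrawal and sedation. None concerns ALT.

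**Baseline.** For safety assessments, SAP 5.1.3 states that "the Pre-SUBLOCADE baseline will be the last non-missing value prior to the administration of SUBLOCADE". That is one value per subject.

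**Post-dose sampling.** Table 1 schedules liver tests at Day 8 and EOT only. The weekly-visit text in Protocol 4.1 reads as if they are taken at every weekly visit ("A blood sample for NMP PK assessment and a blood sample for LFTs will also be collected"), which would make four. Unscheduled repeats come on top.

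**Analysis.** SAP 5.5.8.5 counts subjects meeting each row, and the counts "will be summarized at pre-SUBLOCADE baseline and during the SUBLOCADE treatment period using assessments at both scheduled and unscheduled visits". The row beginning "ALT >3 × ULN (and bilirubin ≤ 2 × ULN", together with the row for bilirubin above 2 × ULN, captures every ALT above 3 × ULN. No rise from baseline, absence at baseline or confirmation is required. The SAP calls the rows protocol-specified, but the symptom condition of review criterion 2 and the persistence condition of criterion 3 (Protocol 8.2.7.3) are not carried over, so one value is enough. The same section summarises change from baseline for scheduled tests and lists all liver data.

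**The concern.** The entry limit and the lowest ALT row sit at the same value, so subjects may start next to the line that defines a case. Some may already be over it when dosed, because the screening test can be up to 30 days old and the Day 1 result does not gate the injection.

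Two things then blur the treatment-period total. First, a subject above 3 × ULN both before and after dosing is in both totals, and the table does not show that it is the same person. Second, the comparison is uneven: one chance to cross at baseline, two or more afterwards.

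Hepatic effect is a documented risk of this product (Protocol 1.2.5), the study has no control arm, and this is the only planned categorical summary of the liver tests. With 15 subjects, one case prints as 1/15 = 6.7%. A reader who compares the two columns may see a rise where nothing has changed.

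**Working it through.** **The plan's own figures.** The documents give no expected value for the liver count. Their only probability table (SAP Table 5, Protocol Table 4) uses the binomial with n = 15. For example, 1 − 0.90^15 = 0.794 and 1 − 0.95^15 = 0.537, both as printed. All 24 cells agree within 0.001.

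**Step 1: the asymmetry, without assuming any ALT distribution.** Let p be the chance that one value from a subject with unchanged ALT exceeds 3 × ULN. The baseline count uses p. The treatment-period count uses 1 − (1 − p)^k for k independent values, which is at least p for any k of 1 or more. With k = 2 (Table 1) it approaches 2p when p is small. Extra repeats raise it further.

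**Step 2: one subject with constant true ALT.** Assume log-normal variation with coefficient of variation CV, so σ = √ln(1 + CV²) and p = 1 − Φ(ln(3/μ)/σ), where μ is usual ALT in multiples of ULN. The CV is not in the documents, so 10%, 20% and 30% are shown. Worked case, μ = 2.5 and CV 20%: σ = 0.198, ln(3/2.5)/σ = 0.921, p = 0.179, and 1 − 0.821² = 0.325.

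Chance of being counted in the treatment period, k = 2 / k = 4:

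| Usual ALT (× ULN) | CV 10% | CV 20% | CV 30% |
|---|---|---|---|
| 1.5 | <0.1% / <0.1% | <0.1% / 0.1% | 2% / 4% |
| 2.0 | <0.1% / <0.1% | 4% / 8% | 16% / 29% |
| 2.5 | 7% / 13% | 33% / 54% | 46% / 71% |
| 2.9 | 60% / 84% | 68% / 90% | 70% / 91% |

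The problem lies with subjects who enter at roughly 2 to 3 × ULN.

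**Step 3: a population, no drug effect.** The simulation draws log-normal true ALT with median 0.6 to 1.3 × ULN, geometric SD 1.8 to 2.2, and within-subject SD of log ALT 0.2 to 0.4. Subjects are kept if screening is below 3 × ULN, and then have one baseline and two post-dose values. All of these are assumptions.

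- Counted in the treatment period: 0.4% to 12.7%.
- Ratio to the baseline count: about 1.6 to 1.8.
- Share of those counted who were already above 3 × ULN at baseline: 17% to 39%.
- Illustrative case (0.8 / 2.2 / 0.3): 4.0% in treatment against about 2.5% at baseline, or 15 × 0.040 = 0.6 against 15 × 0.025 = 0.4 expected subjects. With geometric SD 2.0 instead, the treatment figure is 3.3%, or 0.5 subjects.

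**Step 4: what each added display does.** CV 20%, k = 2, no drug effect:

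| Usual ALT (× ULN) | As written | Also baseline ≤ 3 × ULN | Also ≥ 2 × own baseline |
|---|---|---|---|
| 2.0 | 4.0% | 3.9% | 0.6% |
| 2.5 | 32.5% | 26.7% | 1.2% |
| 2.9 | 67.7% | 38.5% | 1.2% |

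A new-onset condition removes continuing elevation but leaves most chance crossings. In the illustrative population it lowers 4.0% only to about 2.7% (0.6 to 0.4 subjects of 15). The multiple of own baseline is what exposes chance crossings. The factor of 2 is used here only to show this and is not proposed as a rule.

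**The case against.** The strongest reply is that the data are already visible. SAP 5.5.8.5 lists every liver value chronologically, SAP 5.1.5 presents listings by subject, and with about 15 dosed subjects each case can be checked against its own baseline. This stands, and it makes the point minor. It does not remove it: SAP 1.1 records that this table was added so that the data would be summarised and not only listed, and the summary leaves the link to the listing.

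A reader might infer that the SAP presents pre-existing elevations as caused by the injection. It does not. The section counts subjects meeting the rows in each period and calls none of them new or drug-related. Attribution runs through adverse events, where SAP 5.5.2 counts a pre-existing event as treatment-emergent only if it worsened. That route depends on the investigator judging a value clinically significant, so it does not link the laboratory counts themselves.

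A reader might also want the total replaced by new-onset cases only. The documents do not support that. A subject going from 3.1 to 4.9 × ULN worsens within one row and would drop out. The result would also be harder to set beside the plain rates in Protocol 1.2.5 (12.4%, 5.4% and 4.0%), for which no baseline condition is mentioned.

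Finally, applying the 4.0% placebo rate to 15 subjects gives 1 − 0.96^15 = 46% for at least one case. It is tempting to read this as the false-case rate here. It is not: that rate comes from a six-dose study, and the documents do not say how many of those elevations were new.

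**Conclusion.** The point holds as a minor weakness in a descriptive safety table. The two totals are not linked within subject and are not like for like, and the treatment-period total mixes three kinds of elevation. The direction follows from the sampling plan alone: more values after dosing than before give a higher expected count with no drug effect.

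The size does not follow from the documents. The range of 0.4% to 12.7% (15 × 0.004 = 0.06 to 15 × 0.127 = 1.9 subjects of 15) reflects assumed ALT distributions and within-subject variation. Its upper end needs a median ALT of 1.3 × ULN, and at a usual ALT of 1.5 × ULN or below the effect is at most 4% per subject under the assumed CVs. No key endpoint is affected.

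**What to change.** In SAP 5.5.8.5, keep the present counts and thresholds and add:

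1. A shift table of pre-SUBLOCADE baseline category by worst post-dose category, in subjects with a baseline and at least one post-dose value. The existing rows overlap (a subject at 6 × ULN with normal bilirubin meets two of them), so use exclusive ALT bands at the existing cut-points and show the combined ALT and bilirubin row separately.
2. Beside each treatment-period total, the number who did not meet that row at baseline.
3. Worst post-dose ALT as a multiple of the subject's own baseline, per subject and summarised, so that chance crossings and worsening within a row can both be seen.
4. A note that the rows do not carry the symptom and persistence conditions of the protocol's review criteria.

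The number of scheduled post-dose liver tests in Protocol Table 1 and in the weekly-visit text of Protocol 4.1 should be reconciled, since it sets how many chances each subject has to be counted.

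The cost is SAP wording and one extra descriptive table from data already collected. Entry limits, thresholds and clinical review actions are unchanged.

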5.5.8.6 Urine Drug Screen (UDS) qualitative and TimeLine Follow Back (TLFB)

For each visit after Screening, data from the qualitative UDS results entered in the eCRF and TLFB will be combined to derive the number and percentage of subjects with positive opioid use, using observed data. The derivation will be applied according to Table 9.

Table 9 Opioid Use Derivation Based on eCRF Qualitative UDS and TLFB Results at a Given Visit

		TLFB Opioids		
		Missing	Did not use	Use
UDS Opioids	Missing	missing	negative	positive
	Negative	negative	negative	positive
	Positive	positive	positive	positive

For this analysis, opioids will include the eCRF results for opioids, buprenorphine (TLFB only), methadone, fentanyl, oxycodone, and morphine. If the result for any of these are positive, the subject will be considered positive for opioids.

The usage of individual substances collected via the UDS and TLFB will be listed.

5.5.8.7 Urine Drug Screen (UDS) Central Laboratory (Day 1)

The results collected via the central laboratory UDS on Day 1 will be listed.

5.6 Subgroup analyses

No subgroup analyses are planned for this study. However, where specified above for key endpoints and where sample size permits, the following stratification variables will be utilized:

- Number of TM BUP doses during the induction phase (1 dose, ≥ 2 doses)
- Number of TM BUP doses during SUBLOCADE treatment phase (0 dose, ≥ 1 dose)
- Enrollment (i.e., first induction dose of TM BUP) before or after re-training on 08Oct2019

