9.10 Compliance

All study drugs will be administered in the clinic and documented in the source and recorded in the eCRF.

SUBLOCADE compliance will be assessed by inspecting the injection site for evidence of attempted removal of the depot by the subject, documented in the source and recorded in the eCRF. Likewise, surgical removal by a physician will be documented in the source and recorded in the eCRF. See Section [10.7](#) for details on reporting depot removal.

Use of prohibited concomitant medications will be evaluated per the Concomitant Medication assessment outlined in the [Table 1](#) and [Table 2](#), documented in the source and recorded in the eCRF.

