1.1 Version History

Table 1 SAP Version History Summary					
SAP Version	SAP Approval Date	Associated Protocol	Protocol Amendment Approval Date	Change	Rationale
1.0	09Sep2019	Amendment 1	14Aug2019	Not Applicable	Original version
2.0	19Dec2019	Amendment 1	14Aug2019	Described the COWS total score increase of ≥ 6 key endpoint in terms of the cumulative event rate.	To align with updated main analytical approach as Kaplan-Meier.
				Defined the evaluable subjects as having COWS assessments for the key timepoints.	To align with updated main analytical approach of survival analysis.
				Clarified definition of Full Analysis Set.	To align with updated main analytical approach of survival analysis.
				Clarified definition of PK Analysis Set.	To state number of concentration samples required for inclusion.
				Clarified definitions of baseline.	Clarification.

SAP Version	SAP Approval Date	Associated Protocol	Protocol Amendment Approval Date	Change	Rationale
				Defined analysis phases.	To clarify analysis with respect to different study phases.
				Changed description of disposition summary.	To align with analysis phases.
				Added summary of entry criteria failed.	To facilitate reporting by supplementing the listing of failed entry criteria.
				Changed main analytical approach for COWS total score increase of ≥ 6 to Kaplan-Meier using key timepoints. Added stratification sensitivity analysis for number of TM BUP doses post-SUBLOCADE and enrolment before/after re-training.	To account for missing COWS assessments in the first 48 hours post-SUBLOCADE, which was unexpected. Evaluate impact of stratification variables on response.
				Added a sensitivity analysis of COWS total	In consideration of potential for informative missing COWS

SAP Version	SAP Approval Date	Associated Protocol	Protocol Amendment Approval Date	Change	Rationale
				score increase of ≥ 6 utilizing event adjudication.	assessments in the first 48 hours post-SUBLOCADE.
				Corrected the equation for COWS AUC and clarified details of the calculation, including times used and normalization.	Correction and clarification.
				Clarified analysis of change from baseline COWS total scores and OC-VAS scores.	To align with clarification of baseline definitions.
				Clarified definition of precipitated withdrawal following induction dose of TM BUP.	To align with clarification of baseline definitions.
				Clarified calculation of AUC_{inf} for NMP	Clarification.

Table 1 SAP Version History Summary					

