5.1.4 Definition of Analysis Phases

Screening phase: starts from the date of screening visit and ends at the date/time of the first TM-BUP dose for induction.

Induction phase: starts from the date/time of the first TM-BUP dose for induction and ends at the date/time of SUBLOCADE injection or TM-BUP ET visit.

SUBLOCADE treatment phase: starts from the date/time of SUBLOCADE injection through the date of last visit in the study (EOT or EOS, whichever is applicable).

The overall treatment period for the study is the combination of induction and SUBLOCADE treatment phases.

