5.3.2 COWS Total Score Increase by ≥ 6 - Main Analytical Approach

The cumulative event rate for COWS Total Score increase by ≥ 6 from the pre-SUBLOCADE value will be estimated via the Kaplan-Meier method (1958), using the 5 key timepoints, 1, 6, 12, 24 and 48 hours after SUBLOCADE administration (i.e., time=0). Note that for the 1-hour key timepoint the event is referred to as precipitated withdrawal. A subject will be considered in the risk evaluation set at a specific key timepoint if the subject had a pre-SUBLOCADE COWS assessment and either 1) an increase in COWS by ≥ 6 from the pre-SUBLOCADE value within the current time interval (from the previous key timepoint to the current key timepoint), or 2) had a COWS assessment at the current key timepoint and all the prior key timepoints. If a subject has missing COWS assessment at one or more above key timepoints (1, 6, 12, 24 and 48 hours after SUBLOCADE administration), the subject is censored at the last key timepoint prior to the first missing timepoint.

The values for the event occurrence, time, and censoring parameters are assigned sequentially for the subject disposition events according to the order and criteria in Table 7.

Table 7 Parameters for Kaplan-Meier Method

Order of assignment	Disposition Event	Event of COWS Total Score Increase by ≥ 6	Time (hours)	Censored
1	An increase in COWS total score by ≥ 6 from the pre-SUBLOCADE value at any timepoint (scheduled or unscheduled) within 48 hours after SUBLOCADE injection	Yes	Nominal time of the first key timepoint on or after the COWS assessment meeting an increase in COWS total score by ≥ 6 from the pre-SUBLOCADE value	No
2	Missing COWS assessment at a key timepoint and without an increase in COWS total score by ≥ 6 from the pre-SUBLOCADE value within 48 hours	No	Nominal time of last key timepoint prior to the first missing key timepoint (i.e., 0, 1, 6, 12 or 24)	Yes
3	Completed COWS assessment at 1, 6, 12, 24, and 48 hours and without an increase in COWS total score by ≥ 6 from the pre-SUBLOCADE value within 48 hours	No	48	Yes

A Kaplan-Meier plot of the cumulative event rate from time=0 to 48 hours will be produced.

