5.3.3 COWS Total Score Increase – Sensitivity Analyses

5.3.3.1 Stratification Variables

If sample size permits, the cumulative event rate analysis will be repeated for each of three stratification variables: number of TM BUP doses during induction phase (1 dose, ≥ 2 doses) and during SUBLOCADE treatment phase (0 dose, ≥ 1 dose), and by enrollment before or after re-training (see [Section 5.6](#)).

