5.3.6 Normalized AUC for COWS Total Score Post-SUBLOCADE Injection – Sensitivity Analysis

The normalized AUC analysis described in [Section 5.3.5](#) will be repeated, stratified by number of TM BUP doses during induction phase (1 dose, ≥ 2 doses) and during SUBLOCADE treatment phase (0 dose, ≥ 1 dose), and by enrollment before or after re-training ([Section 5.6](#)).

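### The post-injection TM BUP stratum is counted to EOT/EOS, so a dose given after the 1 to 48 h COWS outcomes have closed can set it

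*SAP*

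**What the plan says.** - **Stratum.** SAP 5.6 names three variables for the key endpoints. One is "Number of TM BUP doses during SUBLOCADE treatment phase", split into none and at least one. The others are the number of induction doses and enrolment before or after the re-training date.
- **Counting window.** SAP 5.1.4 says the SUBLOCADE treatment phase "starts from the date/time of SUBLOCADE injection through the date of last visit in the study", that is, EOT or EOS. No section shortens this window for the stratum.
- **Use for the event rate.** SAP 5.3.3.1: "If sample size permits, the cumulative event rate analysis will be repeated for each of three stratification variables". The underlying Kaplan-Meier analysis (SAP 5.3.2) is built "using the 5 key timepoints, 1, 6, 12, 24 and 48 hours after SUBLOCADE administration".
- **Use for AUC.** SAP 5.3.6 says the normalized AUC analysis "will be repeated, stratified by number of TM BUP doses during induction phase", and then adds the post-injection count and the re-training split. The AUC intervals end at the same five times.
- **Purpose.** The SAP version history (1.1) gives the reason for adding the stratification in version 2.0: "Evaluate impact of stratification variables on response".
- **How a post-injection dose can arise.** Protocol 4.1: "Supplemental TM buprenorphine (after SUBLOCADE administration) may only be permitted after discussions with the medical monitor". Protocol 9.7 and 9.9 repeat this, and none of the three states a time limit.

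**The concern.** A stratification variable that is meant to show an influence on an outcome has to be settled before the outcome, or at least independently of it. This one need not be. A TM BUP dose on Day 15 cannot change COWS in the first 48 hours, yet under the SAP's definition it moves the subject from one curve to the other, back to time 0. For the 1-hour endpoint, any dose after the first hour does the same.

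The dependence may also run from outcome to stratum. Protocol 4.1 mentions supplemental TM BUP directly after the text on treating withdrawal that follows the injection, so a subject whose COWS has risen may be the one who is given it.

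At stake is the reading of one sensitivity table. A difference between the strata, or the lack of one, could be taken to show what supplemental TM BUP does to withdrawal, when it reflects who was dosed and when.

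**Working it through.** The plan gives no figure for this stratum. Its only design calculation, the chance of at least one event in 15 subjects at a true rate of 10%, reproduces as 1 − 0.9^15 = 79.4% (SAP Table 5). It does not bear on the point.

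**1. The two windows.** The outcomes close at 48 h at the latest. The stratum is counted for 28 days (EOT) or 42 days (EOS, Day 43). The outcome window is 48/(28 × 24) = 48/672 = 7.1%, or 48/(42 × 24) = 48/1008 = 4.8%, of the counting window. These are shares of time, not of doses.

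**2. Whether a dose can fall after 48 h.** It can, as an exception. Protocol Table 1 marks study drug administration only at the Injection visit. Protocol 9.7 lists supplemental TM BUP under prohibited therapies, subject to discussion with the medical monitor. Protocol 9.10 adds: "All study drugs will be administered in the clinic and documented in the source and recorded in the eCRF". EOS is a telephone contact. Later clinic contacts exist (Days 8, 15, 22 and 29), but no TM BUP is scheduled at them.

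**3. The other two strata.** The induction phase ends at the injection, and enrolment is dated by the first induction dose. Both are fixed before the outcome starts and are unaffected.

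**4. Illustration of a late dose.** All counts are assumed: 15 subjects with complete COWS, 2 with an event by 48 h, and 2 dosed within 48 h, 1 of whom has an event. With complete COWS and no censoring before 48 h, the Kaplan-Meier estimate at 48 h equals the simple proportion, events divided by subjects in the stratum.

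| Doses after 48 h | At least one dose | No dose |
|---|---|---|
| None | 1/2 = 50.0% | 1/13 = 7.7% |
| One, to an event-free subject | 1/3 = 33.3% | 1/12 = 8.3% |
| One, to the other subject with an event | 2/3 = 66.7% | 0/12 = 0% |

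The 48-hour data are the same in every row. A 48-hour limit on the count returns all three rows to the first. The effect on AUC was not quantified.

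**5. What a 48-hour limit leaves open.** A dose at 30 h still enters the strata for the 1, 6, 12 and 24 h endpoints, and a dose within 48 h may still follow the COWS rise.

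**6. Why a fixed rule of counting only doses before the event is no remedy.** An event-free subject has the full 48 hours in which to be dosed. A subject with an event has only the time up to it. Assume a 10% event rate, dosing in 10% of event-free subjects, no effect of TM BUP, and every dose in a subject with an event given after that event. The dosed stratum then holds 0.90 × 0.10 = 0.09 of subjects and no events (0%). The undosed stratum shows 0.10/0.91 = 11.0%. That gap is immortal-time bias alone. The rule also has no meaning for AUC.

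**The case against.** The best defence is that the table matters little and that the route to error is narrow. The analyses are sensitivity analyses, SAP 2 rules out testing, SAP 5.6 says no subgroup analyses are planned and uses the strata only where numbers allow, and the operative sections make no causal claim. SAP 5.5.1 already counts TM BUP doses separately by phase. SAP 5.5.2 lists dose times alongside COWS, SAP 5.3.9 plots each subject, and SAP 5.3.3.2 adds external adjudication. All of this stands and keeps the weight low. It does not repair the definition: a programmer following SAP 5.1.4 would count a Day 15 dose, and the sample-size condition has no threshold.

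Four stronger readings are tempting, and the documents do not support them.

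- A reader might infer that the weekly visits are planned occasions for TM BUP. The schedule shows none.
- A reader might infer that post-injection withdrawal is the reason for supplemental doses. Protocol 4.1 provides non-opioid treatment for withdrawal and states no indication for supplemental TM BUP. The link rests on adjacent sentences, so it is possible, not established. No dosing frequencies are given from which to size it.
- A reader might infer that late doses create a false difference. In the illustration, a late dose to an event-free subject narrows the contrast. Only the dose to the subject with an event widens it.
- A reader might infer that the main results are biased. The unstratified Kaplan-Meier and AUC analyses do not use this variable.

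It is also fair to say that deleting a prespecified stratum from an open-label study's SAP raises its own question of selective reporting. That argues for limiting the count first.

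**Conclusion.** The point holds as a gap in definition. The post-injection TM BUP stratum is counted well past the close of the outcomes it divides and may partly result from them, so it cannot serve the purpose given in the version history. The documents report no number of supplemental doses. The size therefore rests on assumed counts, on complete COWS (the plan expects missing assessments and censoring), and on the event rate alone. Under those assumptions a single late dose visibly changes the table, in either direction. The consequence is confined to one conditional, untested table for each of the two endpoints. It is worth correcting because the correction is cheap, but it does not threaten the study's main estimates.

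**What to change.** In SAP 5.6, 5.3.3.1 and 5.3.6, define the post-injection stratum by TM BUP doses given within 48 hours after the SUBLOCADE injection. Label the stratified tables descriptive. State that no effect of TM BUP on COWS can be inferred from them, because doses may follow the COWS rise and because doses after 1, 6, 12 or 24 hours still enter the strata of those earlier endpoints. In SAP 5.5.1, split the post-injection dose counts at 48 hours, and read dose times against COWS in the listing already planned in SAP 5.5.2. Leave the induction-dose and re-training strata as they are.

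Dropping this one stratum, with the reason documented, is an acceptable alternative. A fixed classification by doses before the event should not be used.

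The cost is a few words in three SAP sections and one split table row. The dose times are already needed for the planned listing. The downside is a smaller stratum with at least one dose.
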